PROTOCOL: Probiotics for Chalaziosis Treatment in Children

Approval number: 07/19

Approved by CTS of Department of Medicine and Health Sciences “V. Tiberio” of Molise University on the 07 th January, 2019

The trial was registered at clinical trials.gov as NCT04322500 on the 25 th March, 2020 (“retrospectively registered”)

PURPOSE: Human gut holds over 100–1000 microbial species, which primarily modulate the host internal environment and thereby, play a major role in host health. Supplementation with probiotics has shown promising results against various enteric pathogens thanks to their unique ability to compete with pathogenic microbiota for adhesion sites, to alienate pathogens or to stimulate, modulate and regulate the host's immune response by initiating the activation of specific genes in and outside the host intestinal tract. [R. G. Kerry et al, *Benefaction of probiotics for human health: A review*, 2018] In recent years, intestinal microbiota emerged as a candidate responsible for providing innate stimuli to prime the immune system, and its contribution to pathogenesis of autoimmune diseases has been intensively studied. Clinical studies support a link between changes in gut commensal microbiota (‘dysbiosis’) and human autoimmune diseases including rheumatoid arthritis, spondyloarthritis, lupus, diabetes, inflammatory bowel disease and multiple sclerosis [McLean MH, Dieguez D Jr, Miller LM, et al. *Does the microbiota play a role in the pathogenesis of autoimmune diseases? Gut* 2015; Scher JU, Littman DR, Abramson SB. *Microbiome in inflammatory arthritis and human rheumatic diseases. Arthritis Rheumat* 2016; Ochoa-Reparaz J, Kasper LH. *The influence of gut-derived CD39 regulatory T cells in CNS demyelinating disease. Transl Res* 2017]. Moreover, animal studies on autoimmune uveitis in rodents have unraveled strong associations of gut microbiota with disease. Also ocular conditions such as chalazia are linked to dysbiosis [*Infective and Inflammatory Eyelid Disorders: Conventional and Unconventional Therapies to Maintain Eye Health and Avoid Lid Surgery*; A. L. Giacomini, *EC Ophthalmology* 2016]. Moreover, it is well known that any eating disorders such as excessive use of saturated fats, can result in a change in the composition of the secreted fat of the Meibomian glands, making it less fluid. So it becomes difficult to spill the glandular secretion leading to chalazia formation. The

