correlation between inflammatory conditions of the conjunctival membrane, lacrimal dysfunctions and an intestinal immune condition featuring dysbiosis are pathophysiological conditions of great interest and are currently analysed. To the best of our knowledge there are no studies on probiotics supplementation in chalaziosis. Moreover, several evidence demonstrate that probiotics may play a role in the prevention and treatment of different conditions not only in adults, but also in children. In the latter population acute diarrhea is an important application of probiotics (Lactobacillus rhamnosus and Saccharomyces boulardii reduce the duration of gastroenteritis by approximately 24 h) [*The good bugs: the use of probiotics in pediatrics. Sansotta N, Curr Opin Pediatr.2019*]. Hence, this study aims to define the possible beneficial impact of probiotics on children suffering from chalaziosis.

DESIGN: This is a simple blind observational study. Paediatric patients affected by chalaziosis will be recruited. These patients will be divided in two groups, one receiving a supplementation with probiotics and the other one not. Prior to enrollment in the study all patients will undergo a complete ophthalmological examination which includes : visual acuity test, slit lamp for annexes and anterior segment assessment, ocular fundus examination, intra ocular pressure measurement. Subsequently a complete ophthalmological evaluation will be done weekly during the first month and then monthly until the healing. The ophthalmologist will be masked.

ATTENDED RESULTS: Altering the intestinal microbioma with specific probiotics can ameliorate the clinical course of chalaziosis by re-establishing intestinal and immune homeostasis. So, we expect to observe a reduction or absence of the recurrences of chalazia.

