CONCLUSIONS: The use of probiotics for clinical health benefits is a fascinating area of research that the present era has yet to explore. Some of the elite properties of probiotics, such as anti-pathogenicity, anti-diabetic, anti-obesity, anti-inflammatory, anti-cancer, anti-allergic, and angiogenic activities and their effect on the brain and central nervous system are quite known. This study will provide further informations on probiotics and human health. Moreover, the intestinal microbiota are potentially crucial in spreading inflammatory disease of the eye, and can be targeted for therapeutic effects. So, throughout our study will be highlighted that probiotics supplementation could increase the effectiveness of traditional therapies in reducing recurrences of chalaziosis in an easy and feasible way.

Statistical Analysis Plan

Mann Whitney U test will be used in order to analyze if there will be a significant difference between the two groups in:

- Time taken for complete resolution of the chalazion
- Number of recurrences

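### If children are not allocated at random, the SAP's only analysis, an unadjusted Mann-Whitney test, could report an initial difference between the groups as a probiotic effect, or hide a real one

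*Combined protocol and SAP*

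**What the plan says.** The DESIGN section states: "This is a simple blind observational study". It goes on: "These patients will be divided in two groups, one receiving a supplementation with probiotics and the other one not". It gives no allocation rule, random or otherwise, and the ophthalmologist is masked. The same section schedules baseline data: "Prior to enrollment in the study all patients will undergo a complete ophthalmological examination", and this includes "slit lamp for annexes and anterior segment assessment".

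The Statistical Analysis Plan is one sentence with two outcomes: "Mann Whitney U test will be used in order to analyze if there will be a significant difference between the two groups in" time to complete resolution and number of recurrences. It names no covariate, stratification, matching, baseline comparison or sensitivity analysis.

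The aim is to learn what probiotics do. Under ATTENDED RESULTS the authors write "we expect to observe a reduction or absence of the recurrences of chalazia". Besides dysbiosis, the one patient-level factor that the protocol links to chalazion formation is diet. PURPOSE says that "excessive use of saturated fats, can result in a change in the composition of the secreted fat of the Meibomian glands", but diet is not listed as recorded or used.

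**The concern.** A two-sample rank test asks whether outcomes differ between the groups, not why. A difference can be attributed to the probiotic only if the groups were comparable at the start. Random allocation would secure that on average, but the plan does not claim it. Masking the examiner protects the assessment of outcomes and does nothing for comparability at entry.

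If the way children enter each group is related to their initial disease, the error can go either way. A milder probiotic group can produce a significant result with no effect, and a more severe one can bury a real benefit. Both SAP outcomes are exposed.

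**Working it through.** **No figure to reproduce.** The documents give no sample size, effect size, significance level or power. Every input below is assumed, for illustration only.

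**Inputs.** 15, 30 or 50 children per group; two-sided 5% test. Healing time is exponential, with mean 4 months in severe and 2 months in mild disease. Mean recurrences are 1.0 and 0.5 over one equal period, which the documents do not define. Healing is recorded at the next visit, on the DESIGN schedule ("weekly during the first month and then monthly until the healing"), with no censoring. Simulations use 10,000 replicates per cell unless stated; the simulation standard error is about 0.2 points at 5% and 0.4 at 20%.

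**Step 1: what the imbalance does.** Let the groups be 30% and 70% severe, with no probiotic effect. Mean healing times are 0.3×4 + 0.7×2 = 2.6 months and 0.7×4 + 0.3×2 = 3.4 months. A mild case heals before a severe one with probability 0.5/(0.5 + 0.25) = 2/3. The chance that a child in the milder group heals first is therefore 0.49×2/3 + 0.09×1/3 + 0.42×1/2 = 0.567, where the test assumes 0.5. At 40% versus 60% it is 0.36×2/3 + 0.16×1/3 + 0.48×1/2 = 0.533.

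**Step 2: false-positive rate by formula.** Under the null the standard error is √[(2n+1)/(12n²)], that is 0.107, 0.075 and 0.058 for n = 15, 30 and 50. With z = (probability − 0.5)/SE, the rejection rate is about Φ(z − 1.96) + Φ(−z − 1.96). At 30% versus 70% and n = 50, z = 0.0667/0.0580 = 1.149 and the rate is 21.0%.

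| Severe share | Formula, n = 15 / 30 / 50 | Simulation, n = 15 / 30 / 50 |
|---|---|---|
| 30% v 70% | 9.5 / 14.4 / 21.0% | 9.0 / 14.0 / 20.3% |
| 40% v 60% | 6.1 / 7.3 / 8.9% | 5.3 / 7.3 / 8.7% |
| 45% v 55% | 5.3 / 5.6 / 5.9% | 5.1 / 5.5 / 6.3% |
| equal | 5% | 4.9 / 4.9 / 4.9% |

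The simulation adds visit rounding and a continuity correction. At 30% versus 70%, 94–99% of the false positives favour the milder group. For recurrences at that split, simulated rates are 8.5 / 13.0 / 19.8% with Poisson counts and 6.2 / 9.3 / 12.2% with overdispersed counts.

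**Step 3: a hidden effect.** Suppose the probiotic truly doubles the healing rate. With both groups half severe, the chance that a probiotic child heals first is (2/3 + 2/3 + 0.5 + 0.8)/4 = 0.658. If the probiotic group is 70% severe and the other 30%, it is 0.21×2/3 + 0.21×2/3 + 0.49×0.5 + 0.09×0.8 = 0.597. Simulated Mann-Whitney power falls from 31 / 56 / 79% to 14 / 25 / 38%.

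**Step 4: what stratification recovers.** This is the van Elteren test (a stratified Mann-Whitney) for time to resolution at 30% versus 70%:

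| Recorded item agrees with true severity | False positives, n = 15 / 30 / 50 | Power in step 3, n = 15 / 30 / 50 |
|---|---|---|
| always | 4.9 / 4.8 / 5.1% | 28 / 54 / 74% |
| 85% of the time | 6.0 / 7.3 / 9.4% | 20 / 37 / 56% |
| 70% of the time | 8.0 / 11.3 / 15.9% | 15 / 28 / 43% |

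A stratified log-rank test behaves similarly: 5.5 / 5.1 / 5.2% false positives with a perfect item, 9.4 / 13.0 / 18.5% with 70% agreement. At 40% versus 60% (4,000 replicates), Mann-Whitney gave 5.6 / 7.5 / 8.6%; van Elteren gave 4.9 / 5.8 / 5.9% with 85% agreement and 5.1 / 6.8 / 7.8% with 70%.

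**Step 5: balanced groups, as random allocation gives on average.** For the doubled healing rate, Mann-Whitney power is 31.2 / 55.8 / 78.9%. Van Elteren gives 33.3 / 60.4 / 82.3% with a perfect item and 30.8 / 55.7 / 78.9% with 70% agreement. The gain is at most 60.4 − 55.8 = 4.6 points.

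**The case against.** The strongest reply is that the gap lies in allocation, not in the test. The word observational may be loose. A study that divides children into groups, gives one a supplement and masks the examiner reads like assignment by the investigators. If that assignment is random, the Mann-Whitney test is valid and adjustment adds little. This stands, and it is why stratification is recommended only if allocation is not random. It does not remove the point, because assignment by the study need not be random and the documents do not say which it is.

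Three further objections also stand:

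- Nothing in the documents shows that the number of chalazia or age predicts healing or recurrence. Any stratifier needs the investigators' justification.
- Outside the larger imbalance the benefit is small. At 40% versus 60% with 70% agreement, stratifying removes less than one point (8.6 − 7.8 = 0.8 at 50 per group).
- The resolution outcome is worded for a single chalazion. Stratifying by single versus multiple raises the question of when a child with several counts as healed.

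A reader might infer that the groups are known to be unbalanced, or that the study is definitely non-randomised. The documents support neither. They report no baseline data, and they leave the allocation method unstated.

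**Conclusion.** The concern holds conditionally. The plan calls the study observational, states no random allocation, and offers only a test that uses no baseline information. As written, it gives no ground for reading a group difference as an effect of the probiotic. If allocation is not random and initial disease is prognostic, the test can mislead in either direction.

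The size cannot be known. With the assumed twofold difference in healing time and 15 to 50 per group, false positives for time to resolution run from about 5% to 9% at a 40% versus 60% split and 9% to 21% at 30% versus 70%. These rates are not estimates for this trial: the splits, the prognostic ratio and the sample sizes are all assumed.

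Nor do the documents support the reading that the Mann-Whitney test is wrong in itself or that an adjusted analysis is needed whatever the allocation. Under random allocation it keeps its 5% size, and stratification is worth at most about 5 points of power. This should be put right; confidence is medium because the allocation method is unknown.

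**What to change.** 1. State how the two groups are formed.
2. Define and record one baseline disease item at the planned pre-enrolment slit-lamp examination, for example single versus multiple chalazia, or another item that the investigators justify as prognostic. Tabulate it and age by group, and dietary fat if it can be asked simply.
3. If allocation is not random, make the primary comparison of each outcome stratified by that item: van Elteren for both, or a stratified log-rank test for time to resolution. Keep the unadjusted Mann-Whitney test as a sensitivity analysis, and describe results as associations adjusted only for the recorded item. If allocation is random, the unadjusted test may stay primary and the stratified test is optional.
4. If number of chalazia is the stratifier, define resolution for a child with several chalazia in the same way in both groups.

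The cost is one item transcribed from an examination already scheduled, a baseline table and a few SAP sentences. The analysis becomes slightly more complex, and protection is limited if the item is a weak proxy for severity. A common period for counting recurrences is a separate matter and is not part of this point.
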